9.3.2 DEFINITION OF SERIOUS ADVERSE EVENTS (SAE)

A SAE is any AE occurring at any dose that results in any of the following outcomes:

- Death
- Is life-threatening (places the participant, in the view of the site PI, at immediate risk of death from the AE as it occurred)
- Inpatient hospitalization or prolongation of existing hospitalization (hospitalization is defined as an inpatient admission, regardless of length of stay, even if hospitalized as a precautionary measure for continued observation)
- A permanent, persistent, or significant disability (substantial disruption of the ability to conduct normal life

functions). A medically significant AE that may jeopardize the participant and may require medical or surgical intervention to prevent one of the outcomes listed in this definition

Events NOT considered to be **Serious** are:

- Hospitalization for treatment, which was elective or pre-planned, for a pre-existing condition that did not worsen
- Treatment on an emergency, outpatient basis for an event NOT fulfilling any of the definitions of serious given above and NOT resulting in hospital admission
- An event that, had it occurred in a more serious form, might have caused death
- A sign, symptom, or event that is noticeable but easily tolerated.
- An event does not significantly influence performance or prevent the participant from carrying on with their usuall life activities.

9.3.3 CLASSIFICATION OF AN ADVERSE EVENT

9.3.3.1 SEVERITY OF EVENT

The severity of adverse changes in physical signs or symptoms will be classified as follows:

- Grade 1 (Mild): Asymptomatic or mild symptoms; clinical or diagnostic observation only; intervention not indicated.
- Grade 2 (Moderate): Minimal, local or noninvasive intervention indicated; limiting age- appropriate instrumental ADL (Activities of Daily Living).
- Grade 3 (Serious): Medically significant but not immediately life-threatening; hospitalization or prolongation of hospitalization indicated; disabling; limiting self-care ADL.
- Grade 4 (Life-threatening): Consequences; urgent intervention indicated.
- Grade 5 (Death): Event is a direct cause of death.

A sign, symptom, or event that causes serious discomfort to the participant and significantly affects clinical status or the ability to perform normal daily life activities. Treatment intervention is warranted.

9.3.3.2 RELATIONSHIP TO STUDY INTERVENTION

An event is related to the research if, in the opinion of the UAB/UM investigator, it was more likely than not to be the result of the interventions and interactions used in the research (i.e., there is a reasonable possibility that the event may have been caused by participation in the research).

The determination of the likelihood that the study drug caused the AE will be provided by the site PI. The site PI's signature and date on the source document and eCRF that supports the causality noted on the AE form, ensures that a medically qualified assessment of causality was done. The assessment of relationship will be reported by the site PIs according to his/her best clinical judgment the following scale of criteria may be used as a guidance (not all criteria will be present in order to be indicative of a drug relationship).

Definitely Related to the Research:

- There is evidence of exposure to the study drug
- The temporal sequence of the AE onset relative to administration of the study drug is reasonable
- The AE is explained by the study drug

Probably Related to the Research:

- There is evidence of exposure to the study drug
- The temporal sequence of the AE onset relative to administration of the study drug is reasonable
- The AE is more likely explained by the study drug than by another cause

Possibly Related to the Research:

- There is evidence of exposure to study drug
- The temporal sequence of the AE onset relative to administration of the study drug is reasonable
- The AE could have been due to another equally likely cause

Unlikely Related to the Research:

- There is evidence of exposure to the study drug
- There is another more likely cause of the AE
- There is no temporal relationship to study drug

Unrelated to the Study Drug:

- There is no evidence of exposure to the study drug
- There is another more likely cause of the AE
- There is no temporal relationship to study drug

For all presumed Serious/SAE a study safety event report will completed and submitted to the Data Safety Monitoring Board (DSMB) (see MOOP Section 2.m) and IRB after validation of event. Monitoring of these outcome events will begin as soon as a study participant is enrolled and will continue until the end of the observation period. The DSMB will provide independent oversight and act in an advisory capacity to monitor research participant safety and data quality and to alert the NIAMS to potential issues.

9.3.3.3 EXPECTEDNESS

Expected potential AEs Associated with MMF (see also section 2.3.1)

- Gastrointestinal: Nausea and vomiting (12%), diarrhea
- Hematologic & oncologic: Leukopenia (renal transplant: > 50%; RA: 28%), neoplasia (renal transplant: 3% (other than lymphoma), 0.5% (lymphoma)), thrombocytopenia
- Hepatic: Hepatotoxicity, increased serum alkaline phosphatase, increased serum bilirubin, increased serum transaminases
- Infection: Increased susceptibility to infection (renal transplant 20%; RA <1%; includes bacterial, fungal, protozoal, viral, opportunistic, and reactivation of latent infections)

Expected potential AEs associated with Pegloticase (see also section 2.3.1)

During pre-marketing controlled clinical trials, infusion reactions were reported in 26% of patients treated with pegloticase 8 mg every 2 weeks. During pre-marketing controlled clinical trials, anaphylaxis was reported with a frequency of 6.5% for patients treated with pegloticase. For the purposes of this study, these events shall be defined as follows:

IR (see Section 8.3.8.1) not attributable to another cause that occurs during or within 2 hours after the

infusion of pegloticase will be defined as an AE. Other cases that occur outside of the 2-hour window may also be categorized as an IR as per site PI discretion.

- Anaphylaxis will be defined using the National Institute of Allergy and Infectious Diseases (NIAID)/ Food Allergy and Anaphylaxis Network (FAAN) criteria: acute onset of an illness (minutes to several hours) with involvement of the skin, mucosal tissue, or both (e.g., generalized hives; pruritus or flushing; urticarial, and angioedema (of lips, tongue, or uvula) and at least one of the following:
 - Hypotension (i.e., systolic blood pressure < 90 mm Hg or > 30% decrease from that person's screening)
 or associated symptoms of end-organ failure (e.g., hypotonia [collapse], syncope, incontinence)
 - Respiratory compromise (e.g., dyspnea, bronchospasm, stridor, reduced peak expiratory flow, hypoxemia)

Expected potential AEs Associated with Colchicine (see also section 2.3.1)

Participants taking colchicine for gout flare prophylaxis may experience gastrointestinal intolerance which may lead to nausea, persistent diarrhea, and/or gastrointestinal bleeding. The most commonly reported side effects for the prophylaxis of gout were diarrhea (23%) and pharyngolaryngeal pain (3%).

Other rare AEs associated with colchicine include:

- Neutropenia, leading to an increased risk of infection
- Anemia
- Myalgia or myositis
- Alopecia
- Pruritus
- Neuropathy
- Oligospermia

While taking colchicine participants should avoid eating grapefruit and Seville oranges or drinking grapefruit juice or Seville orange juice. Consumption can increase their chances of experiencing serious side effects.

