3.3 RISK/BENEFIT ASSESSMENT

3.3.1 KNOWN POTENTIAL RISKS

The known risks for participants as a result of participation in the RECIPE study are summarized below. This includes risks associated with the proposed study medications as well physical, psychological, social, economic, and/or legal risks from participating in this study.

- 1. Participants may experience pain from the needle used during phlebotomy, as well as possible bruising and soreness at the phlebotomy site. Pain following injection and bruising will subside over time.
- 2. Participants may experience some anxiety in completing questionnaires about their gout. The questionnaires should take <20 minutes to complete. Anxiety following completion of the questionnaires should subside over time.
- 3. Immediate and longer-term drug specific risks for all study drugs All study drugs to be tested/administered in the RECIPE study are FDA approved for use in various conditions. Risk associated with each are listed below and taken from package inserts and published literature (see Appendices 4, 5, and 6):

a. Mycophenolate Mofetil (MMF) (Oral ingestion).

i. Immediate Risks

- Nausea—20%; often subsides over time and following discontinuation of MMF
- Persistent diarrhea—36%; Subsides over time and following discontinuation of MMF
- Gastrointestinal bleeding requiring hospitalization—1.7%-5.4%
- o Neutropenia—2-3.6%; Subsides over time following discontinuation of MMF
- Decreased immune function and corresponding increased susceptibility to bacterial, viral, fungal, and protozoal infections, including opportunistic infections—1%-10%
- Other symptoms, occurring at rates of 1% to 10%, include hypertension, hypotension, tachycardia, chills, pain, musculoskeletal discomfort, and rash/acne

ii. Longer Range Risks

- Mycophenolate mofetil may increase the risk of developing lymphoma (a type of cancer of white blood cells) and other malignancies, particularly of the skin—1%-10%. Participants will be monitored for safety including malignancies during the study. To reduce the chances of skin cancer, participants will be encouraged to wear protective clothing and using an effective sunscreen when exposed to sunlight.

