4 OBJECTIVES AND ENDPOINTS

OBJECTIVES	ENDPOINTS	JUSTIFICATION FOR ENDPOINTS
Primary		
To assess efficacy of daily mycophenolate mofetil (MMF) to attenuate immunogenicity to pegloticase.	Proportion achieving and maintaining serum urate ≤ 6 mg/dL through 12 weeks, compared to concurrent controls.	Serum urate ≤ 6 mg/dL is slightly below the urate solubility threshold and this threshold has been the accepted standard for nearly all modern gout trials. 23-26 If the serum urate goal is not maintained before or at the 12 week mark, it will be assumed that the participant has developed clinically relevant anti-pegloticase antibodies and they will receive no further infusions. This assumption and subsequent discontinuation of pegloticase is consistent with the protocol of large phase III randomized controlled trials and the product label.
To assess the incidence and types of adverse events/infusion reactions potentially associated with a dual therapy regimen of pegloticase and MMF.	Incidence and Type of Adverse Events (AEs), Serious Adverse Events (SAEs), and Participant withdrawals due to AEs, anaphylaxis, and Infusion Reactions (IRs)	Safety profile is important because of the addition of an immune modulatory agent (MMF) that has potential of causing serious AEs
Secondary		
To assess durability of immune modulation after discontinuation	Absolute change in serum urate from baseline to wk 24; week 12 to 24 Proportion of participants with serum urate < 6 mg/dL through week 24; week 12 to 24	Assess if the efficacy of the short course of MMF continues following discontinuation.
To identify and characterize pegloticase immune response by immunoglobulin	Anti-pegloticase antibody isotypes (IgG/IgM), specificity, and titers	We anticipate that the primary Ab produced will be IgM anti-pegloticase but some participants, who will likely be the non-

OBJECTIVES	ENDPOINTS	JUSTIFICATION FOR ENDPOINTS
		responders will produce
		both IgM and IgG
		antibodies at earlier onset
To assess patient reported outcomes	PROs using PROMIS and Gout Impact score	To assess impact of the
(PRO)		intervention on patient
		reported outcomes
Tertiary/Exploratory		
Not applicable		

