9.2 SAFETY AND OTHER ASSESSMENTS

Physical examination: A complete physical examination (e.g., height and weight, organ systems, motor or vision assessment, or other functional abilities) will be performed at Visit 1, Visit 11, and Visit 17. and targeted physical examination with joint assessment will be performed at Visit 3, 5, 7-10, 1217.

Vital signs: consisting of heart rate, respiratory rate, blood pressure (noting the position in which it was obtained), and body temperature will be performed at Visit 1, 2, 3, 5, 7-17.

Biological specimen collection: Following Screening Visit, Visits 3, 8, 11, 14, 17-20, and any unscheduled visits a biospecimen will be collected for measurement of antibody response. Additionally, in the event a participant experiences an infusion reaction during a specimen will be collected, as high titer anti-pegloticase antibodies have been associated with a loss of responsiveness to pegloticase and increased infusion reactions.

Assessment of study intervention adherence: Infusion logs and pill counts (during the first 12 weeks) will be kept measure participant adherence to the study intervention.

Assessment of adverse events: Significant findings that occur after administration of pegloticase which meet the definition of an AE will be recorded in the medical record and on the Adverse Events care report forms.

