9.3.8 EVENTS OF SPECIAL INTEREST

9.3.8.1 INFUSION REACTIONS (IRS)

As described in section 8.3.3.3 during pre-marketing controlled clinical trials, infusion reactions (IR) were reported in 26% of patients treated with pegloticase 8 mg every 2 weeks. IRs will be defined as any infusion-related AE or cluster of temporally-related AEs, not attributable to another cause, which occur during or within 2 hours after the infusion of

pegloticase. Other AEs that occur outside of the 2-hour window following the infusion may also be categorized as an IR per site PI discretion. Signs and symptoms of the IR, and treatments administered, will be documented in the medical record and in the eCRF. Examples of AEs not considered possible IRs include but are not limited to: laboratory abnormalities that are unlikely to have occurred during or within 2 hours following the infusion (e.g., anemia, hypercholesterolemia), gout flares, most infectious diseases, or the recurrence or worsening of a known chronic medical problem identified in the participant's medical history.

IRs are not uncommon when biological agents are administered by IV infusion. Therefore, all participants will receive pre-treatment prophylaxis consisting of at least an antihistamine and corticosteroid prior to each infusion of pegloticase (see **Table 2**). In order to standardize this regimen, participants will take fexofenadine (60 mg, PO) the night before and again on the morning of the infusion with acetaminophen (1000 mg, PO) Prior to the infusion, hydrocortisone (200 mg, IV) will be administered and a at minimum, a targeted physical exam will be performed. The name, dose, route, date, and time of administration of each prophylactic medication will be recorded in the medical record and in the CRF.

Table 2. Infusion Reaction Prophylaxis

Night Before Infusion	Morning of Infusion	Following Arrival at Infusion Clinic
Participant takes:	Participant takes:	Abbreviated physical examination to include:
Fexofenadine (60 mg) PO	Fexofenadine (60 mg) PO	Dermatological – Noting Any Rashes
	Acetaminophen (1000 mg) PO	Chest – Noting Breath Sounds
		Vital Signs
		Start IV and Administer hydrocortisone (200 mg)
		Initiate Drug Infusion

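### The anaphylaxis definition takes its percentage fall in systolic pressure from a screening value 4 to 26 weeks old, although a same-day pre-infusion value is recorded (minor)

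*Combined protocol and SAP*

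**What the plan says.** Section 9.3.3.3 sets the study's own definition of anaphylaxis. Skin or mucosal involvement of acute onset is always required, together with at least one further feature. One route is low blood pressure, defined as "systolic blood pressure < 90 mm Hg or > 30% decrease from that person's screening". The hypotension item also admits end-organ symptoms: "or associated symptoms of end-organ failure (e.g., hypotonia [collapse], syncope, incontinence". The other route is "Respiratory compromise (e.g., dyspnea, bronchospasm, stridor, reduced peak expiratory flow, hypoxemia". Neither of these two needs a reference blood pressure.

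The schedule of activities (Section 2.3, Table 1) places screening at Week -4 and the infusions at two-week intervals from Week 0 (Visit 3) to Week 22 (Visit 16). Section 9.2 has "Vital signs: consisting of heart rate, respiratory rate, blood pressure (noting the position in which it was obtained") at Visits 1, 2, 3, 5 and 7 to 17, which covers every infusion visit. In Section 9.3.8.1, Table 2 puts vital signs under "Abbreviated physical examination to include", on arrival at the infusion clinic and ahead of hydrocortisone and the infusion.

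Section 4 names the event in the co-primary safety endpoint: "Participant withdrawals due to AEs, anaphylaxis, and Infusion Reactions (IRs"). That wording leaves open whether anaphylaxis is reported as an incidence or as a reason for withdrawal. Section 10.4.3 makes the safety analysis largely descriptive, with no test on anaphylaxis.

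**The concern.** An infusion reaction is an acute event, so the natural reference for a fall in pressure is the reading taken just before that infusion. The written rule uses a reading from before the run-in instead. The fall it measures is then the acute change plus whatever the resting pressure has done over 4 to 26 weeks. If resting pressure has dropped since screening, a modest acute fall can meet the 30% limit. If it has risen, a large acute fall can miss it.

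At stake is the count of a rare event named in the co-primary safety endpoint. Sections 10.4.1 and 10.4.2 make the recommendation for a full-scale trial conditional on safety. With so few cases expected, each should be classified on the best reading available.

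**Working it through.** The plan states no figure on this point, so there is nothing to reproduce.

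**Age of the reference.** Age = infusion week + 4. Over the twelve infusions (Weeks 0, 2, ..., 22) this gives 4, 6, ..., 26 weeks. If the shared Screen/Run-In column heading in Table 1 is read to include Visit 2 (Week -2), the range is 2 to 24 weeks.

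**When the reference matters.** The blood-pressure limb is met when the nadir is below the cut-off

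cut-off = max(90, 0.70 × reference systolic pressure).

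The percentage rule adds something only when 0.70 × reference > 90, that is, reference > 90/0.70 = 128.6 mmHg. The two references disagree only when the nadir lies between their two cut-offs. So the class cannot change if the nadir is below 90, or if both references are 128.6 or lower. It also cannot change if respiratory compromise or end-organ symptoms are present, or if skin and mucosal signs are absent.

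**Both directions are possible.**

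| Screening | Pre-infusion | Nadir | Screening cut-off | Same-day cut-off | Fall from screening | Fall from pre-infusion | Counts with |
|---|---|---|---|---|---|---|---|
| 150 | 125 | 104 | 105 | 90 | 46/150 = 30.7% | 21/125 = 16.8% | screening only |
| 125 | 155 | 105 | 90 | 108.5 | 20/125 = 16.0% | 50/155 = 32.3% | pre-infusion only |

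**Expected number of cases.** Section 3.2 gives 5% and Section 9.3.3.3 gives 6.5%. For 32 participants: 32 × 0.05 = 1.6 and 32 × 0.065 = 2.08. One case is 1/24 = 4.2 percentage points in the MMF arm or 1/8 = 12.5 points in the placebo arm.

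**How often the two references disagree.** The documents give no blood-pressure variability, so this part rests on assumptions: mean systolic pressure 125 to 140 mmHg, between-person SD 12, visit-to-visit SD 8 to 16, and acute falls uniform between 10% and 45%. Screening pressure is capped at 160, the entry limit in Section 6.2. In simulation:

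- 4% to 19% of falls that meet the same-day rule are missed by the screening rule;
- 5% to 13% of falls that meet the screening rule do not meet the same-day rule.

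Applied to 2.08 cases, the upper ends give 2.08 × 0.19 = 0.40 of a case missed and 2.08 × 0.13 = 0.27 of a case added. These overstate the effect, because the simulation covers the blood-pressure limb alone and treats every case as resting on it.

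**The case against.** The strongest reply is that the reference is explicit, objective and the same in both arms, and that Section 9.3.4 already takes the condition at screening as baseline for adverse events. On this view the check measures disagreement between two rules rather than error. Most true anaphylaxis would also qualify through dyspnea, collapse or a pressure below 90. Nothing goes unreported either: a reaction not labelled anaphylaxis is still an adverse event. It is an infusion reaction if its signs are ones "which occur during or within 2 hours after the infusion of" pegloticase, or later at the site investigator's discretion.

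Much of this stands. It limits the point to a minority of reactions, and the worked cases need shifts of 25 and 30 mmHg between the two readings. It does not justify the choice of reference. Section 9.3.4 separates pre-existing conditions from new ones, which is a different purpose from measuring an acute fall. Listing all adverse events keeps the record complete but does not correct the anaphylaxis count. The documents also use baseline in more than one sense: Section 6.2 applies it to Visits 1 and 3 for blood pressure, and Section 9 labels Visit 3 as baseline.

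A reader might infer that MMF biases the comparison, because it starts after screening and Section 3.3.1 says of it "Other symptoms, occurring at rates of 1% to 10%, include hypertension, hypotension". The documents do not support this. The MMF list names both directions with no net effect. The pegloticase list in the same section gives hypertension and hypotension at 3% each, and both arms receive pegloticase. MMF is last dispensed at Week 10, so the later infusions have no concurrent MMF. Drift that differs by arm is not excluded, but it is not shown.

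**Conclusion.** The point holds as a minor one. The definition uses a reference 4 to 26 weeks old when a same-day value is recorded. Reactions with skin or mucosal signs can then be classified wrongly either way if there is no respiratory compromise or end-organ symptom, the nadir is at least 90 mmHg, and at least one reference exceeds 128.6 mmHg.

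The age of the reference, the 128.6 threshold and the two worked cases follow from the documents and arithmetic. The frequency does not: it depends on assumed variability, and under those assumptions it is well under one case in 32.

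Two stronger readings are tempting. One is that events are in fact misclassified; the documents show only that they can be. The other is that a single reclassified case would decide the trial's conclusion. With 1.6 to 2.1 cases expected, one case would be a large share of the count. But such a case is unlikely, the historical rates may not apply here, and the safety analysis is descriptive with all events listed.

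**What to change.** In Section 9.3.3.3, define the decrease of more than 30% relative to the pre-infusion systolic pressure recorded at the same infusion visit, and make the change before unblinding. Limit it to classification and reporting under Section 10.4.3; it changes nothing in how participants are managed. If continuity with the present text is wanted, keep the screening-based classification as a sensitivity listing, so that any case whose class depends on the reference is visible.

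The cost is one phrase in the protocol and one derivation rule. Section 9.2 and Table 2 already provide the reading, so no new measurement or visit is needed.
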